12.4 Biospecimen Management

Specimens will be received by JHU from other participating sites, per protocol calendar, and then stored at JHU. Specimens will be sent to collaborating universities (Stanford University and Mayo Clinic) and vendors for analysis as per protocol appendices and materials transfer agreements.

The rectal swab samples will be used for DNA sequencing of the microbiome. The fundamental DNA sequencing technology is common and available at most institutions, but the bioinformatic pipelines and expertise needed to ensure good data quality and analysis is niche. [name] (UCSD) and [name] (UCSD) are experts in this regard to help with end-to-end sample handling, sample preparation, sequencing, and data analysis.

The role of [name], [name], and their team at UCSD will be to process the swab samples and perform DNA sequencing on the microbiota. The role of the JHU team in this collaboration will be to provide outcome data with no obvious PHI from the RAVENS trial to allow for clinical correlations to be made based on results of the DNA sequencing done at UCSD. No physical materials will be transferred back to Hopkins. The analysis will be performed at UCSD and the results will be shared with the JHU team once completed to facilitate writing of a manuscript. [name] team will be leading the manuscript writing.

The JHU Office of Research Administration is initiating a Material Transfer Agreement with UCSD regarding this data analysis.

13. REGULATORY CONSIDERATIONS

13.1 Protocol Review and Amendments

Information regarding study conduct and progress will be reported to the Institutional Review Board (IRB) per the current institutional standards.

Any changes to the protocol will be made in the form of an amendment and must be approved by the IRB prior to implementation.

13.2 Informed Consent

The investigator (or his/her designee) will explain to each subject the nature of the study, its purpose, the procedures involved, the expected duration, the potential risks and benefits involved and any discomfort it may entail. Each subject will be informed that participation in the study is voluntary, that she may withdraw from the study at any time, and that withdrawal of consent will not affect her subsequent

medical treatment or relationship with the treating physician(s) or institution. The informed consent will be given by means of a standard written statement, written in non-technical language, which will be IRB approved. The subject should read and consider the statement before signing and dating it, and will be given a copy of the document. No subject will enter the study or have study-specific procedures done before his/her informed consent has been obtained.

In accordance with the Health Information Portability and Accountability Act (HIPAA), the written informed consent document (or a separate document to be given in conjunction with the consent document) will include a subject authorization to release medical information to the study sponsor and supporting agencies and/or allow these bodies, a regulatory authority, or Institutional Review Board access to subjects' medical information that includes all hospital records relevant to the study, including subjects' medical history.

13.3 Ethics and GCP

This study will be carried out in compliance with the protocol and Good Clinical Practice, as described in:

1. ICH Harmonized Tripartite Guidelines for Good Clinical Practice 1996.
2. US 21 Code of Federal Regulations dealing with clinical studies (including parts 50 and 56 concerning informed consent and IRB regulations).
3. Declaration of Helsinki, concerning medical research in humans (Recommendations Guiding Physicians in Biomedical Research Involving Human Subjects, Helsinki 1964, amended Tokyo 1975, Venice 1983, Hong Kong 1989, Somerset West 1996).

The investigator agrees to adhere to the instructions and procedures described in it and thereby to adhere to the principles of Good Clinical Practice that it conforms to.

14. STATISTICAL CONSIDERATIONS

14.1 Endpoints

14.1.1 Primary Objective

To determine progression-free survival in patients with oligometastatic (three metastases or less) hormone sensitive prostate cancer and at least one bone metastasis who have been treated with SABR *versus* SABR + Radium-223.

14.1.2 Secondary Objectives

- To describe the toxicity of SABR and SABR + Radium-223 delivered for the population enrolled using grading with CTCAE v. 4.0
- To determine local control at 12-months after SABR and SABR + Radium-223 in patients with oligometastatic disease.

- To assess time to locoregional progression, time to distant progression, time to new metastasis and duration of response after randomization to SABR *versus* SABR + Radium-223.
- To assess ADT-free survival (ADT-FS) of this patient population after randomization defined as the time interval between the day of randomization and the initiation of ADT. ADT will typically be initiated on progression and/or development of new metastases.
- To assess quality of life following SABR *versus* SABR + Radium-223 arms. Brief Pain Inventory form which will be filled out by the patient at the treatment response intervals outlined above.

14.2 Sample Size/Accrual Rate/Follow-Up

The primary endpoint will be progression-free survival (PFS). Data from STOMP and ORIOLE on this patient population indicate that $\geq 50\text{-}60\%$ would show progression as defined above within a 12-month period from SABR, and a median PFS around 10 months. (72-74). We hypothesize that the addition of radium-223 will be able to reduce the risk of progression by 50%. A sample size using a 1:1 randomization scheme of 30 patients per arm will provide 80% power to detect an increase of median PFS from 10 months to 20 month (corresponding to hazard ratio 0.5) with type I error = 0.1, using one-sided log-rank test. The calculation assumes 18 months of accrual time with an additional follow-up of 12 months after the last patient is randomized. To account for 5% early drop out, we will randomize a total of 64 patients (32 per arm).

There will be no interim analysis for futility, since the progression endpoint will not have been reached by a meaningful number of patients before full accrual.

Follow-up (Every 3-6 months for 24 months or until death)

Patients will be followed for 2 years after Day One of trial or until death. Patients withdrawn from the study because of AEs will be followed until the adverse event has either resolved or stabilized. Reasons for premature withdrawal should be determined and noted.

14.3 Stopping Guidelines

This study will monitor site-specific grade 4/5 toxicity in the SABR + Radium-223 arm. If it becomes evident that the proportion of grade 4/5 toxicity at specific sites convincingly exceeds 20%, the study will be halted for a safety consultation. Specifically, we will apply a Bayesian toxicity monitoring rule that suspends the enrollment if the posterior probability of toxicity being larger than 20% threshold is 75% or higher. The monitoring rule uses Beta (0.5, 5.5) as prior distribution. This means that our prior guess of the proportion of toxicity is 8.3%, and there is

90% chance that this proportion is 0.04%-30.6%. The monitoring will start from the first patient, and the decision rule for safety stopping is as follows:

Stop if:

# grade 4/5 toxicity >=	3	4	5	6	7	8	9	10
Out of # patients	3 - 5	6 - 10	11 - 14	15 - 18	19 - 23	24 - 27	28 - 32	33 - 36

The operating characteristics of the stopping rule are shown below and are based on 5000 simulations:

True AE rate	% simulated trials declaring unsafe	Average sample size
0.10	2.4	31.5
0.2	29.5	26.8
0.25	52.6	22.8
0.3	74.9	18.4
0.35	89.2	14.2

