6.8 Duration of Therapy

Within three weeks of the initial treatment planning imaging study, SABR will be administered in a 1-5 fractions to each treated site (within 60 days from randomization) of the study and coincides with delivery of fraction 1.

Within four weeks of randomization to the SABR + Radium-223 arm, men will receive their 1st of 6 monthly infusions of radium-223.

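### The stated operating characteristics of the toxicity stopping rule assume each man's outcome is known before the next man enters; with a radium course of about six months the rule can stop appreciably later, depending on a window and denominator that section 14.3 does not define.

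*Combined protocol and SAP*

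**What the plan says.** Section 14.3 opens with "This study will monitor site-specific grade 4/5 toxicity in the SABR + Radium-223 arm". The rule "suspends the enrollment if the posterior probability of toxicity being larger than 20% threshold is 75% or higher", and "The monitoring rule uses Beta (0.5, 5.5) as prior distribution". The section continues: "The monitoring will start from the first patient, and the decision rule for safety stopping is as follows". A two-row table then gives, for every count of patients from 3 to 36, the number of grade 4/5 toxicities that triggers a stop. Of its performance the section says "The operating characteristics of the stopping rule are shown below and are based on 5000 simulations". At true rates of 10, 20, 25, 30 and 35% the stated chance of declaring the arm unsafe is 2.4, 29.5, 52.6, 74.9 and 89.2%, and the stated average sample size is 31.5, 26.8, 22.8, 18.4 and 14.2.

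The timing facts are elsewhere. Section 6.4 gives radium as six injections at four-week intervals. Section 6.8 says that within four weeks of randomization "men will receive their 1st of 6 monthly infusions of radium-223". Section 14.2 states "The calculation assumes 18 months of accrual time" and "we will randomize a total of 64 patients (32 per arm"). Section 6.9, under the heading on accrual, anticipates three years.

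Section 14.3 gives no toxicity observation window. It does not say whether the patient count means men enrolled, treated or fully observed, and it does not address men still in mid-course. Section 14.6 counts toxicity from first treatment with no end, and section 10.3 records events for two years.

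**The concern.** A rule that compares toxicities with patients, checked from the first man onward, behaves as tabled only if each man's result is in hand when he is counted. Here a man's radium exposure lasts about half a year while others keep entering. If men in mid-course are counted as toxicity-free, the observed rate is diluted and suspension comes later. If they are left out unless they have had an event, the observed rate is inflated and false stops rise. The rule protects men by halting entry, so what is at stake is how many more are enrolled into an unsafe combination before it acts, and whether the monitoring committee is relying on figures that the design does not deliver.

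**Working it through.** **1. Boundaries.** With x toxicities among n men, the posterior is Beta(0.5 + x, 5.5 + n − x). The boundary is the smallest x for which the probability above 0.20 is at least 0.75. For example, 3 of 5 gives Beta(3.5, 7.5) and 0.795 (stop); 3 of 6 gives Beta(3.5, 8.5) and 0.742 (continue). All tabled boundaries for n = 3 to 36 reproduce, as do the prior mean, 0.5/6 = 8.3%, and the 90% prior interval.

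**2. The stated operating characteristics.** An exact patient-by-patient binomial recursion, with at most 32 men and each outcome known before the next entry, gives:

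| True rate | Unsafe, stated | Unsafe, exact | Average N, stated | Average N, exact |
|---|---|---|---|---|
| 10% | 2.4 | 2.6 | 31.5 | 31.4 |
| 20% | 29.5 | 29.7 | 26.8 | 26.8 |
| 25% | 52.6 | 53.4 | 22.8 | 22.7 |
| 30% | 74.9 | 74.9 | 18.4 | 18.3 |
| 35% | 89.2 | 89.1 | 14.2 | 14.4 |

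With 5,000 simulations the standard error of a percentage near 50 is √(0.5 × 0.5/5000) = 0.7 points, so the table is what immediate outcomes produce.

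**3. Men in mid-course.** First to sixth injection is 5 × 4 = 20 weeks, or 24 weeks (about 5.5 months) with the last cycle, and the start may be up to four weeks after randomization. Taking six months, the number entering the arm during one course is 32/18 × 6 = 10.7 with 18-month accrual and 32/36 × 6 = 5.3 with 36-month accrual.

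**4. Staggered entry.** The tabled boundaries were applied in 5,000 simulated trials per cell, with 32 men, random entry over 18 or 36 months, and the rule checked at every entry, event and (where relevant) window completion. Onset times and denominators are assumptions, because the documents give neither. Each cell shows the result at a true rate of 30% / 35%.

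| Denominator, onset, accrual | Average enrolled | Stopped before arm full, % | Ever declared unsafe, % |
|---|---|---|---|
| Section 14.3 as stated | 18.4 / 14.2 | not given | 74.9 / 89.2 |
| Immediate outcomes | 18.3 / 14.4 | about 73 / 88 | 74.9 / 89.1 |
| All enrolled, uniform 0-6 months, 18 months | 26.4 / 23.6 | 45.9 / 66.3 | 67.2 / 85.7 |
| All enrolled, uniform 0-6 months, 36 months | 22.4 / 19.5 | 61.6 / 76.6 | 70.7 / 85.3 |
| All enrolled, within 1 month, 18 months | 19.6 / 15.9 | 69.4 / 85.3 | 73.1 / 88.0 |
| All enrolled, all at month 6, 18 months | 30.7 / 29.4 | 17.7 / 33.1 | 64.9 / 84.9 |
| Event or completed window only, uniform 0-6 months, 18 months | 18.0 / 15.7 | 83.0 / 91.7 | 86.8 / 94.5 |

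The averages and the immediate-outcome row are exact; the other rows carry simulation error. Repeat runs of the third scenario gave 46-48% stopped before full and 67-70% ever declared unsafe at a 30% rate.

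**5. Size.** With all enrolled men counted and uniform onset, the excess over the stated average is 26.4 − 18.4 = 8.0 and 23.6 − 14.2 = 9.4 men at 18 months, and 22.4 − 18.4 = 4.0 and 19.5 − 14.2 = 5.3 at 36 months. With onset within one month at 18 months it is 19.6 − 18.4 = 1.2 and 15.9 − 14.2 = 1.7.

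**6. False stops.** At a true rate of 10%, counting only men with an event or a completed window raises the chance of stopping from about 2.5% to about 8-9% under uniform onset (18-month accrual).

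**The case against.** The strongest reply is that section 14.3 is incomplete rather than unprotective. It does not say that all enrolled men form the denominator, and no passage gives the timing of grade 4/5 events. If events cluster soon after entry, or if only men with an event or a completed window are counted, the rule stops at about the stated point or earlier. That is correct, and a reader should not infer that the rule must stop much later than stated.

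A reader might also set the 46% against the stated 74.9% and infer a loss of nearly 30 points. Those are different quantities: the first is stopping before the arm is full, the second is ever being declared unsafe. Like for like, 73% falls to 46% and 74.9% falls to about 68-70%.

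Other safeguards exist. Serious events go to the coordinating center within 24 hours (section 10.5.1.2), blood counts are checked before each infusion (study calendar), and the monitoring board reviews toxicity at least annually and may recommend ending accrual (section 12.2). These temper any claim that men are unprotected, but they do not correct the table.

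What remains is that the published figures rest on immediate outcomes, and that the rule cannot be applied in only one way as written.

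**Conclusion.** The concern holds in conditional form. That the table corresponds to immediate outcomes is established by exact calculation. That this departs from the trial's own schedule follows from sections 6.4, 6.8 and 14.2. The consequence depends on two things the plan leaves open. With all enrolled men counted and toxicity even over six months, roughly eight to nine more men are enrolled at true rates of 30-35% under 18-month accrual, and four to five more under 36-month accrual. The main loss is in halting entry before it finishes; the eventual chance of crossing the boundary drops by only about 3 to 7 points. With early onset the effect is small. With the narrower denominator the error changes direction, into false stops. The documents do not support saying that the plan lacks the protection it claims; they support saying that its stated performance is not what the design delivers when toxicity is spread over the course. This should be corrected before the rule is relied on.

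**What to change.** In section 14.3, define the toxicity window used by the rule and state who enters the patient count, including how men in mid-course are handled. Re-run the simulation with staggered entry at 18- and 36-month accrual, with early, uniform and late onset. Replace the table with one reporting, for each true rate, the chance of ever being declared unsafe, the chance of stopping before full accrual, and average enrolment.

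One candidate keeps the Beta(0.5, 5.5) prior and the 75% cut-off but weights each man by the fraction of the window completed, with weight 1 once an event occurs. Under uniform onset and 18-month accrual, at a 30% rate, it gives about 74% declared unsafe, about 65% stopped before full, and average enrolment of about 22. It should not be taken as a proven repair, because linear weights suit exactly the uniform onset used to test them. With onset within one month, false stops at a 10% rate rise to about 6.7%; with onset in months 3 to 6, stopping before full at a 30% rate is about 52%. Its performance should be shown over the same range.

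The cost is SAP wording, a short simulation, and average sample sizes that will probably look less favourable. No accrual pause is required by this change.

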14.4 Analysis of Primary Objective

This is a randomized, Phase II trial of SABR *versus* SABR + Radium-223 in oligometastatic hormone sensitive prostate cancer patients. Minimization approach (77) will be applied to ensure balanced assignment to each treatment arm by stratification factors: 1) Institutional; 2)Initial treatment with surgery vs. radiation therapy; 3) Prior hormonal therapy vs. no prior hormonal therapy; and 4) PSADT <6 mos vs. 6-14.9 mos. Baseline PSA level is defined as that measured Day 1 following randomization. Progression is defined as per section 9.6.2.

The primary outcome of interest is PFS, defined as the time from the date of randomization to the date of disease progression or death, whichever happens earlier. For those who are alive and do not have progressive disease, PFS will be censored at the time of the last scan. Kaplan-Meier method will be used to summarize PFS and log-rank test will be used to compare PFS between the two arms. The analysis population includes all randomized subjects based on intent-to-treat principle.

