6.7 Follow-Up Procedures

6.7.1 Blood Draws

Subsequent to randomization, patients will be followed clinically and radiographically. A detailed medical and physical examination with blood draws for PSA, LDH, CBC w/Diff, Serum Chemistry panel (CMP), ctDNA (CAPP-seq), immune cell profiling (ImmunoSEQ), CTCs (EPIC HD-CTC), immunophenotyping, and testosterone will be performed within the first month, months 3, 6 and 12 (from date of randomization) for all patients. Correlatives at outside sites are optional and not mandatory. In-clinic visits are not required otherwise, unless indicated by laboratory tests. For men randomized to the SABR + Radium-223, they will also receive monthly CBCs as per standard of care for radium-223 infusions (within 7-10 days of radium-223 injection). Following 12-months patients will be followed by any physician as per standard of care which may include but not be limited to every 3-6 month clinic visits, laboratory evaluations for PSA and imaging, if appropriate. Further labs and imaging is at the discretion of the treating physician. This information of two year followup will be collected by the clinical study team for all participating sites.

Correlative science blood draws will be performed as above (details for these blood draws are contained within the APPENDIX III-V).

Briefly:

CAPP-Seq: 30-ml whole blood in purple top (EDTA) tubes (see APPENDIX III for details). The blood is stored in a freezer, then shipped in batches as per APPENDIX III. Baseline, months 3, 6 and 12 from randomization for both arms.

EPIC HD-CTC: 4-10 ml Streck Cell-Free DNA BCT tubes (see APPENDIX IV for details). Whole blood is shipped out the same day as it is drawn as per APPENDIX IV. Baseline and day 180 from all men.

ImmunoSEQ: 10-ml whole blood in purple top (EDTA) tubes (see APPENDIX V for details). The patient samples are stored in a 80 Degree Celsius freezer and shipped in batches as per APPENDIX V. Baseline and day 90 from all men.

Immunophenotyping: 2-10-mL whole blood in green top (heparin) tubes (see APPENDIX VIII for details).

Only participating sites that have the resources to do so, will participate in blood draw collection and shipment.

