6.7.2 Imaging

Bone scan and CT/MRI of metastatic site(s) will be at 6- and 12-months for all patients, unless indicated more frequently by clinical or laboratory findings.

If applicable, bone scan and ¹⁸F-DCFPyL (“PyL”) -PET/CT of metastatic site(s) will be at 6 months for all patients, unless indicated more frequently by clinical or laboratory findings. The results of the ¹⁸F-DCFPyL (“PyL”) -PET/CT will be made available to the treating physicians prior to enrollment to determine treatment.

The CT portion of the ¹⁸F-DCFPyL (“PyL”) -PET/CT scans at 6 months will be used to determine radiographic response based on RECIST 1.1 criteria for soft tissue lesions. Similarly, the CT or MRI scans at 6- and 12-months will be used to determine radiographic response based on RECIST 1.1 criteria for soft tissue lesions.

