9.5.5 Clinical Response Parameters

Progression is a composite endpoint defined from the Prostate Cancer Working Group 2 (PCWG2) criteria for metastatic castrate resistant prostate cancer (mCRPC) (75) and our previous trials in a population of men with biochemical failure without metastases (72-74). Progression will be defined as either: 1) a $\geq 25\%$ increase in PSA from nadir (and by ≥ 2 ng/mL), requiring confirmation ≥ 4 weeks later (PCWG2 criteria); and/or, 2) clinical/radiographic-progression defined as symptomatic progression (worsening disease-related symptoms or new cancer-related complications), or radiologic progression (on CT scan: $\geq 20\%$ enlargement in sum diameter of soft-tissue target lesions [RECIST 1.1 criteria]; on bone scan: ≥ 1 new bone lesions), initiation of ADT or death due to any cause, whichever occurs first. Death is considered a severe adverse event here.

Progression Free Survival (PFS) is defined as the time from starting treatment to the time of progression as defined above. Subjects who do not progress will be censored at the time of the last contact.

ADT Free Survival (ADT-FS) is defined as the time from starting treatment to the time of initiation of palliative ADT. ADT will typically be initiated on tumor progression and/or development of new metastases. Subjects who do not start ADT will be censored at the time of the last contact.

Time to Progression (TTP) is defined as the time from starting treatment to the time of first documented tumor progression or new lesions by CT and/or bone scan or initiation of ADT. Subjects who do not progress will be censored at the time of the last contact. In addition, death from any cause will also be censored.

Time to New Metastasis (TNM) is defined as the time from starting treatment to the time of a new documented tumor metastasis by CT and/or bone scan. Subjects who do not progress will be censored at the time of the last contact.

Overall Survival (OS) is defined as the time from starting treatment until death due to any cause. For subjects who do not die, time to death will be censored at the time of last contact.

Locoregional Control (LRC) is defined as the time from starting treatment until local and/or regional relapse is documented

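### Primary PFS has two unreconciled censoring rules, and the last-scan rule pulls the late Kaplan-Meier curve down when event-free men go unscanned after month 12

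*Combined protocol and SAP*

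**What the plan says.** Two current sections define the primary endpoint differently.

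| | Section 14.4 | Section 9.5.5 |
|---|---|---|
| Censoring | "For those who are alive and do not have progressive disease, PFS will be censored at the time of the last scan" | "Subjects who do not progress will be censored at the time of the last contact" |
| Time origin | "defined as the time from the date of randomization to the date of disease progression or death" | "Progression Free Survival (PFS) is defined as the time from starting treatment to the time of progression as defined above" |

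Neither section says which prevails. For the definition of progression, 14.4 says "Progression is defined as per section 9.6.2". No such section exists; section 9 ends at 9.5.6, and the definition is in 9.5.5.

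That definition is a composite: confirmed PSA rise, symptomatic progression, radiologic progression, start of ADT, or death. On imaging, section 6.7.2 says "Bone scan and CT/MRI of metastatic site(s) will be at 6- and 12-months for all patients". After month 12, section 6.7.1 foresees "every 3-6 month clinic visits, laboratory evaluations for PSA and imaging, if appropriate" and leaves further labs and imaging to the treating physician. In section 8, footnotes W (SABR calendar) and Z (radium calendar) require PSA, a limited exam and a medication update at months 18 and 24, but not imaging. Sites taking part in PSMA PET add one repeat scan at about month 12 to 14, depending on which footnote is followed.

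**The concern.** Two analysts following the protocol could report two different primary results, and the choice could be made after the data are seen.

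The rule in 14.4 is also wrong for this composite. A man whose PSA and exam show him event-free at month 24, but who was last scanned at month 12, is censored at month 12. A man with a PSA event at month 20 stays in the risk set until month 20. Whether a man is still counted after month 12 therefore depends on whether he later fails. That is informative censoring, and it makes the late Kaplan-Meier curve fall too fast.

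The hypothesised 20-month radium median lies in the affected period, and section 14.5 commits to reporting median PFS. The 10-month SABR median lies before it. The error therefore tends to hide the doubling that the trial was designed to show. If late scanning differs by arm, the log-rank test is affected too.

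**Working it through.** **Inputs.** Section 14.2 gives medians of 10 and 20 months (HR 0.5), one-sided alpha 0.10, 30 per arm for power and 32 randomized, 18 months of accrual plus 12 of follow-up, and 24 months of follow-up per man. Scans at months 6 and 12 come from 6.7.2; visits at months 18 and 24 come from section 8. *Assumptions:* exponential PFS; each event-free man is scanned with probability p at each of months 18 and 24; events are dated when they occur unless stated.

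**1. The plan's own figure.** With uniform accrual, P(event) = 1 − [exp(−12λ) − exp(−30λ)]/(18λ), which is 0.751 for SABR and 0.509 for radium. Expected events are 30 × (0.751 + 0.509) = 37.8. Schoenfeld requires 4(1.282 + 0.842)²/(ln 2)² = 37.5, so 38. Power is Φ(½√37.8 × 0.693 − 1.282) = 0.80. The stated 80% reproduces.

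**2. The bias by hand (radium arm, every man followed 24 months).** True S(t) = 2^(−t/20), so S(12) = 0.6598, S(18) = 0.5359 and S(24) = 0.4353. A man event-free at month 24 had his last scan at month 24 with probability p, at 18 with p(1 − p), and at 12 with (1 − p)².

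- Risk set just after month 12: R12 = S(12) − S(24) + S(24)[1 − (1 − p)²]
- Up to month 18: KM(t) = S(12){1 − [S(12) − S(t)]/R12}
- Risk set just after month 18: R18 = S(18) − S(24) + p·S(24)
- KM(24) = KM(18) × p·S(24)/R18

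For p = 0.25:
- R12 = 0.2245 + 0.4353 × 0.4375 = 0.4149, and KM(18) = 0.6598 × (1 − 0.1239/0.4149) = 0.463.
- KM reaches 0.5 where S(t) = 0.6598 − 0.4149 × (1 − 0.5/0.6598) = 0.5593, which is t = **16.8** months.
- R18 = 0.1006 + 0.1088 = 0.2094, and KM(24) = 0.463 × 0.1088/0.2094 = **0.24**.

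For p = 0.5, the median is **18.4** and KM(24) = **0.35**. For p = 0, they are 14.5 and 0. For p = 1, they are 20.0 and 0.435, so there is no bias. Simulation gives the same values.

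**3. Analysis at month 30 (staggered entry, 400,000 simulated men).**

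| Censoring rule | Median | S(24) |
|---|---|---|
| Truth | 20.0 | 0.435 |
| Last contact | 19.9 | 0.434 |
| Last assessment of any kind | 18.3 | 0.377 |
| Last scan, p = 1 | 18.3 | 0.377 |
| Last scan, p = 0.5 | 16.5 | 0.270 |
| Last scan, p = 0.25 | 15.1 (15.2 in repeat runs) | 0.163 |
| Last scan, p = 0 | 13.8 | 0.00 |

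The SABR median stays at 10 under every rule. A repeat PET at month 13.5 in every man moves the p = 0.25 and 0.5 medians only to 16.1 and 17.3. A PET at or before month 12 changes nothing.

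**4. Event dating.** If only 10% of events are dated when they occur and the rest at visits, last-scan S(24) at month 30 is 0.21 or 0.33 for p = 0.25 or 0.5. Last assessment gives 0.43.

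**5. The test (one-sided 0.10, 32 per arm, 8,000 trials, SE at most 0.006).**

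| Power | Last contact | Last scan, p = 0.5 | p = 0.25 | p = 0 |
|---|---|---|---|---|
| Month 30, visit-dated events | 0.785 | 0.776 | 0.758 | 0.711 |
| Month 30, dated when they occur | 0.816 | 0.790 | 0.750 | 0.664 |
| Full 24 months | 0.845 | 0.826 | 0.784 | 0.639 |

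Type I error is 0.099 to 0.110 with equal scanning. With SABR scanned at 25% and radium at 50% it is 0.134 to 0.155; reversed, it is 0.060 to 0.075. Last-assessment censoring in the same trials gives 0.096 to 0.106 (6,000 null trials per scenario).

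**The case against.** The contradiction itself is not in dispute; its size is. The documents give no late-scan rate, and the radium calendar marks bone scan and CT/MRI in the follow-up column. If every event-free man were scanned at months 18 and 24, last-scan and last-assessment censoring would coincide. This stands as a limit on size, but footnotes W and Z and section 6.7.1 make late imaging discretionary.

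The medians above assume that events are dated when they occur, whereas PSA and scan events are found at visits. With 10% dated when they occur, the radium median at month 30 reads 24 under last contact or last assessment and 18 under last scan, and the SABR median reads 12 under every rule. The figures change, but the gap between rules remains.

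The effect on the test is small in the visit-dated case (0.79 to 0.76 or 0.78), and the type I error shift needs an assumed imbalance. The discretion wording is the same in both arms, and radiologists are blinded. All true, but blinded reading does not control who is sent for a scan in an unblinded trial.

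Finally, last-assessment censoring appears in neither section, and in the staggered, exactly dated case last contact is closer to the truth. Which of these two is primary is a judgement; last scan should be neither.

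**Conclusion.** The concern holds. Two censoring rules, two time origins and a dead cross-reference stand in current text for the primary endpoint. Under 14.4 as written, the late curve is biased downward whenever event-free men go unscanned after month 12. With 25% to 50% late scanning and events dated when they occur, a true 20-month radium median reads about 15 to 16.5 months at month 30, or 17 to 18.4 with full follow-up. S(24) reads 0.16 to 0.35 instead of 0.435.

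The direction does not depend on the assumed scan rate unless all late scans are done; the size does. With equal scanning the test stays valid and loses little to moderate power, and the bias works against showing a benefit. With unequal scanning its level can move either way.

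The effect of the time-origin conflict was not quantified. Section 6.8 allows SABR "to each treated site (within 60 days from randomization) of the study", so the two clocks can differ by up to about two months. This should be fixed before analysis.

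**What to change.** 1. Delete last-scan censoring from 14.4. In both 14.4 and 9.5.5, censor event-free men at the last protocol assessment able to detect a PFS event (PSA, imaging, or a visit with exam, symptom and ADT review) that showed no progression. Report last-contact censoring as a sensitivity analysis. The reverse order is also acceptable.
2. Use randomization as the time origin in both sections, to match the intent-to-treat population.
3. Correct the reference to 9.6.2 so that it points to 9.5.5.
4. State that imaging-only progression after month 12 may be missed or dated late.

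The cost is wording in two sections. No new data are needed, since PSA and an exam are already required at months 18 and 24. The plan should disclose what remains (radium arm, true S(24) 0.435):

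- **Analysis before all men reach 24 months.** Last assessment reads slightly low: 0.43 or 0.42 if 10% or 30% of events are dated when they occur, and 0.38 (median 18.3) if all are. The residual is zero with full follow-up and all visits attended.
- **Missed visits with contact kept (10% or 25% of men, month-30 analysis).** With 10% of events dated when they occur, last contact reads high (0.455 or 0.485) and last assessment slightly low (0.43 or 0.42). With 30%, the errors are similar and opposite (0.45 or 0.48 against 0.41 or 0.40). This is why both should be reported.
- **Imaging-only progression.** If 25% or 50% of progressions after month 12 show only on imaging and no late scans are done, either rule reads about 0.49 or 0.55.
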